9.5.4 Contraception and Pregnancy

If a subject who received ARCT-021 in this study becomes pregnant or a pregnancy is suspected, or if a male subject who received ARCT-021 in this study makes or believes that his sexual partner has become pregnant with his child during the study, then the Study Center staff must be informed immediately. The pregnancy should be reported in the EDC **within 24 hours** of first learning of the occurrence of the pregnancy. If the EDC is not available, the pregnancy can be initially reported using a paper Pregnancy Notification Form, which should be faxed or emailed to the Sponsor or designee. Follow-up information including delivery or termination should be reported in the EDC within 24 hours if the subject is still enrolled in the clinical trial or via a paper Pregnancy Follow-Up Form if the subject is no longer enrolled in the clinical trial. Pregnancy reporting instructions, including the fax number and email address for submitting paper forms can be found in the Investigator site file for the study.

Payment for all aspects of obstetrical care, child or related care will be the subject's responsibility.

Female subjects: If a suspected pregnancy occurs while on the study in a female subject that has received ARCT-021, a pregnancy test will be performed. If the pregnancy test is positive, the subject will be encouraged to complete the post-treatment follow-up portion of the study to the extent that study procedures do not interfere with the pregnancy. Regardless of continued study participation, the study physician will assist the subject in getting obstetrical care and the progress of the pregnancy will be followed until the outcome of the pregnancy is known (i.e., delivery, elective termination, or spontaneous abortion). If the pregnancy results in the birth of a child, the Study Center and Sponsor may require access to the mother and infant's medical records to obtain additional information relevant to the pregnancy progress and outcome. A longer follow-up may be required if a newborn child experiences a medical condition. Follow-up will be performed to the extent permitted by the applicable regulations and privacy considerations; e.g., pregnancy ICF may be required.

Male subjects: In the event that the female partner of a male subject that has received ARCT-021 becomes pregnant, the progress of the pregnancy of the male subject's partner should be followed until the outcome of the pregnancy is known (i.e., delivery, elective termination, or spontaneous abortion). If the pregnancy results in the birth of a child, the Study Center and Sponsor may follow-up with the mother and may request access to the mother and infant's medical records to obtain additional information relevant to the pregnancy progress and outcome. A longer follow-up may be required if a newborn child experiences a medical condition. Follow-up will be performed to the extent permitted by the applicable regulations and privacy considerations; e.g., partner informed consent form may be required.

9.5.5 Cases of PCR-confirmed COVID-19 or PCR/Serologically Confirmed SARS-CoV-2 Infection Without COVID-19

Any case of PCR-confirmed COVID-19 will be regarded as a Clinical Event of Special Interest (Section 9.3.7) and must be reported to the Sponsor or designee within 24 hours of the site learning of this event.

In addition, CESIs must be reported for all cases detected for up to one year after receipt of vaccination with ARCT-021, including events reported by participants who have early

terminated study ARCT-021-01 or study ARCT-021-02 and participants who did not roll over to the ARCT-021-02 study if these events fall within the 1 year timeframe.

Whilst the subject is enrolled in the study reporting will be performed by completion of a ‘COVID-19 and SARS-CoV-2 Infection Report Form’ in the EDC (Section 9.4.1). For subjects that have terminated early from the study but not withdrawn consent, cases of PCR-confirmed COVID-19 and PCR/serologically confirmed SARS-CoV-2 infection without COVID-19 will be reported via a paper COVID-19 and SARS-CoV-2 Infection Report Form, which should be faxed or emailed to the Sponsor or designee. The reporting instructions, including the fax number and email address for submitting paper forms can be found in the Investigator site file for the study.

The EDC and paper reporting forms will collect the following parameters:

- Whether PCR test and/or anti-nucleocapsid antibody test are positive
- COVID-19 symptoms
- Oxygen saturation on air
- Percent supplemental oxygen required (if any)
- Type of assisted ventilation required (if any)
 - CPAP
 - External Ventilation
 - Invasive Ventilation
 - Other (specify)
- Whether intensive care unit admission required
- Investigations performed:
 - Chest X-ray
 - CT Scan
 - Bronchoscopy
 - Other (specify)
- PCR confirmed COVID-19 disease will be graded as follows:
 - **Mild:** No requirement for supplemental oxygen to maintain oxygen saturation $\geq 93\%$
 - **Moderate:** Oxygen supplementation at a concentration of $< 50\%$ required to maintain oxygen saturation $\geq 93\%$
 - **Severe:** Oxygen supplementation at a concentration of $> 50\%$ or any form of mechanical ventilatory support required

10 STATISTICAL CONSIDERATIONS

Full details of statistical analyses will be described in the Statistical Analysis Plan (SAP) for Study ARCT-021-01. The SAP will be finalized prior to final database lock. Any changes to the methods described in the final SAP will be described and justified as needed in the clinical study report (CSR). An overview is presented below.

10.1 Sample Size Considerations

As this is an open label follow-on study, the sample size is determined by the number of subjects enrolled in the Parent Study that consent to be followed up in this study; therefore, formal sample size calculations are not applicable.

10.2 Populations

Safety Population: All subjects who receive Study Drug in ARCT-021-02 only

Longitudinal Safety Population: All subjects who receive Study Drug in either ARCT-021-01 or ARCT-021-02

Immunogenicity Population: All subjects who receive Study Drug in either ARCT-021-01 or ARCT-021-02 and who have evaluable immunogenicity data following first vaccine administration.

Additional populations may be defined for individual immunogenicity endpoints and will be pre-specified in the SAP.

Within these populations, analyses will also include Cohorts that combine relevant safety and immunogenicity assessments across ARCT-021-01 and ARCT-021-02 according to time since administration of last dose of ARCT-021 (See [Table 5](#)). These cohorts are defined as follows.

Two primary cohorts will be defined:

- Cohort 1: ARCT-021-02 vaccinated participants (those participants who receive ARCT-021 in Study ARCT-021-02, including those who were assigned to receive placebo in the parent study (ARCT-021-01) and those who enter the ARCT-021-02 without detectable neutralising antibody responses at baseline)
 - This cohort will be further subdivided for an exploratory analysis of cohorts:
 - Cohort 1a: Primary vaccination (Those participants whose first ARCT-021 vaccine administration occurs in the ARCT-021-02 study) and
 - Cohort 1b: Booster vaccination (Those participants who received primary vaccination in the ARCT-021-01 study and who receive an additional dose of ARCT-021 in the ARCT-021-02 study)
- Cohort 2: ARCT-021-01 vaccinated participants (those participants who were vaccinated with ARCT-021 in the parent study and who do not receive subsequent vaccination with ARCT-021 in the current extension study).
 - This cohort will be further subdivided for an exploratory analysis of subcohorts:
 - Cohort 2a: Those participants who received ARCT-021 7.5 µg dose as a single dose administration in the parent study (Cohorts D1 and D2)
 - Cohort 2b: Those participants who received ARCT-021 10.0 µg dose as a single dose administration in the parent study (Cohort C)
 - Cohort 2c: Those participants who received alternate doses and schedules of ARCT-021 in the parent study (Cohorts A, B)
 - Cohort 2d: Those participants who receive two-dose schedules of ARCT-021 in the parent study (Cohorts E, F, G, H)

Additional analysis cohorts, if required, will be prespecified in the statistical analysis plan.

Table 5: Grouping of Cohorts and Timepoints Across Studies ARCT-021-01 and ARCT-021-02 for Analysis

	15 days	1 month	2 months	6 months	12 months
Cohorts 1a and 1b (single dose of 7.5 µg in this Study)	Day 15 in ARCT-021-02	Day 29 in ARCT-021-02	Day 57 in ARCT-021-02	Day 169 in ARCT-021-02	Day 365 in ARCT-021-02
Cohort 2a (single dose of 7.5 µg in Parent Study only)	Day 15 in ARCT-021-01	Day 29 in ARCT-021-01	Day 57 in ARCT-021-01	Day 29 in ARCT-021-02	Day 197 in ARCT-021-02
Cohort 2b (single dose of 10 µg in Parent Study only)	Day 15 in ARCT-021-01	Day 29 in ARCT-021-01	Day 57 in ARCT-021-01	Day 29 in ARCT-021-02	Day 197 in ARCT-021-02
Cohort 2c (alternate single dose schedules in Parent Study only)	Day 15 in ARCT-021-01	Day 29 in ARCT-021-01	Day 57 in ARCT-021-01	Day 29 in ARCT-021-02	Day 197 in ARCT-021-02
Cohort 2d (alternate two dose schedules in Parent Study only)	Day 43 in ARCT-021-01	Day 57 in ARCT-021-01	Day 85 in ARCT-021-01	Day 29 in ARCT-021-02	Day 197 in ARCT-021-02

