Subjects that are not receiving ARCT-021 in this study

All participants who received 2 injections of ARCT-021 as part of participation in Cohorts E, F, G, and H in Study ARCT-021-01 and any participant who received 1 injection of ARCT-021 in Cohorts A, B, C, D1 and D2 in Study ARCT-021-01 AND who is seropositive by SARS-CoV-2 PRNT50 neutralising antibody test at screening in this study (ARCT-021-02).

The study comprises an up to a 4-week Screening Period followed by a 9-month observation period. The length of each subject's participation is approximately 10 months from screening to last study visit.

After screening subjects will return for outpatient visits on Days 1, 29, 85, 197 and then 281. The final visit will be on Day 281.

Subjects that do not receive ARCT-021 in this study will not have any further laboratory safety evaluations performed in this study and only Serious Adverse Events (SAE) and Medically Attended AE (MAAE) will be recorded. Subjects will be instructed to contact the study site staff immediately if they experience an adverse event that requires them to seek medical attention or if they become hospitalised.

Subjects receiving ARCT-021

All participants who received placebo as part of participation in Study ARCT-021-01 and any participant who received 1 injection of ARCT-021 in Cohorts A, B, C, D1 and D2 in Study ARCT-021-01 AND who is seronegative by SARS-CoV-2 PRNT50 neutralising antibody test at screening in this study (ARCT-021-02).

Blood and urine samples will be collected for safety evaluations up to 28 days after the last injection of ARCT-021 ([Appendix 1](#)).

Local and systemic solicited and unsolicited AEs will be recorded daily by the subject in a symptom diary for at least 7 days post vaccination and up to 14 days post vaccination if any events are persisting at 7 days (Section [6.2.1](#) and [Appendix 1](#)).

[figure not shown]

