3.2 Study Design

This is an open label study enrolling healthy adult subjects that participated in Study ARCT-021-01 (the Parent Study). Subjects will enter this study approximately 3 months after their final study visit in the Parent Study.

Subjects who received placebo and subjects who received a single injection of ARCT-021 in the Parent Study and are seronegative for SARS-CoV-2 PRNT50 neutralising antibodies at screening will receive a single injection of ARCT-021 in this study at a 7.5 µg dose level.

Subjects who received two injections of ARCT-021 in the Parent Study and subjects who received a single injection of ARCT-021 but are seropositive for SARS-CoV-2 PRNT50 neutralising antibodies at screening will not receive any further injections of ARCT-021 in this study.

ARCT-021 will be administered by IM injection into the lateral aspect of the deltoid muscle of the non-dominant arm.

Subjects should remain at the center for at least 30 minutes for observation following vaccine administration.

Epinephrine for subcutaneous injection, diphenhydramine for intravenous injection, and any other medications and resuscitation equipment for the emergency management of anaphylactic reactions must be available in close proximity in the room where the vaccination is administered.

If the subject experiences a severe reaction following vaccine administration, the CRO Medical Monitor should be contacted as soon as feasible to discuss if additional assessments may be clinically warranted prior to the discharge of the subject from the study center.

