5.2 Exclusion Criteria

1. Significant (as determined by Principal Investigator) noncompliance with the study visits or procedures in Study ARCT-021-01
2. Any subject that received placebo in the Parent Study and who is not willing to receive ARCT-021 in this study.

Only for subjects that will receive ARCT-021 in this study:

- 3 Receipt of any other SARS CoV-2 or other experimental coronavirus vaccine since completion of the Parent Study or planned during this study.

4. Diagnosis of new clinically significant abnormalities in medical history or physical examination since enrolment in the Parent Study, including but not limited to:
 - Respiratory disease (e.g., chronic obstructive pulmonary disease [COPD], asthma) requiring daily medications or oxygen currently or any treatment of respiratory disease exacerbations (e.g., COPD or asthma exacerbation) warranting hospitalization or an emergency room visit or supplemental oxygen.
 - Significant cardiovascular disease (e.g., congestive heart failure, cardiomyopathy, ischemic heart disease), myocarditis or pericarditis.
 - Neurological or neurodevelopmental conditions (e.g., migraines, epilepsy, stroke, seizures, encephalopathy, focal neurologic deficits, Guillain-Barré syndrome, encephalomyelitis or transverse myelitis).
 - New diagnosis of a significant hematologic abnormality (e.g., sickle cell disease, beta thalassemia)
 - New Diagnosis of autoimmune disease as listed by the American Autoimmune Related Disease Association ([Appendix 3](#))
 - Major surgery
5. Screening laboratory results as follows, or any other clinically significant abnormalities in screening laboratory values that would render a subject unsuitable for inclusion
 - ALT, AST, GGT, total bilirubin or alkaline phosphatase, > ULN unless approved by Sponsor Medical Monitor (or designee).
 - Hb <10 g/dL for females and <12 g/dL for males
 - Platelet count < 100x10⁹/L
 - eGFR < 50 ml/min/1.73m² calculated by Modification to Diet in Renal Disease [MDRD] study equation, unless approved by the Sponsor Medical Monitor (or designee)
6. Diabetes that is not, in the opinion of the investigator, adequately controlled with diet +/- antidiabetic medication
7. Use of any prescription or over-the-counter medications within 7 days prior to vaccination, unless approved by the Sponsor Medical Monitor (or designee).
8. Received immunoglobulins and/or any blood or blood products since completion of the Parent Study.

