10.5.4 Immunogenicity Analyses

Assessment of the long-term neutralising and anti-spike protein IgG responses, including seroconversion rates, following vaccination with ARCT-021 is the secondary objective of the study. The assays and study endpoints for these analyses include:

Assays:

- Neutralising antibody responses based on hCoV-19/Singapore/2/2020 isolate:
 - Plaque reduction neutralising titers (PRNT) and/or
 - pseudovirus neutralization test and/or
 - surrogate virus neutralization test (sVNT) and/or
 - microneutralization test.
 - Exploratory: testing using other SARS-CoV-2 isolates may also be performed.
- Binding antibody responses: Total IgG against the full-length SARS-CoV-2 recombinant spike protein and/or spike protein subunits will be assessed using an immune-Luminex and/or ELISA assay.

Endpoints:

- Neutralising and binding antibody responses at Day 29 (6 months after last dose of ARCT-021), Day 197 (12 months after last dose of ARCT-021), Day 281 (15 months after last dose of ARCT-021) for Cohort 2:
- Neutralising and binding antibody responses at Day 1, Day 15, Day 29 (1 month after last dose of ARCT-021), Day 57 (2 months after last dose of ARCT-021), Day 169 (6 months after last dose of ARCT-021), Day 365 (12 months after last dose of ARCT-021) for Cohort 1
- T cell responses (Flow cytometry and ELISpot assays) at Day 29 and Day 197 (Cohort 2)
- T cell responses (Flow cytometry and ELISpot assays) at Day 1, Day 15, Day 29, Day 169, Day 365 (Cohort 1: ARCT-021-02 vaccinated participants)

Descriptive statistics, by assessment time point, will be used to describe all immunogenicity results and further specified in the SAP prior to data analysis. Statistical testing, if performed, will be prespecified in the final SAP and will be exploratory in nature.

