14 APPENDICES

APPENDIX 1: SCHEDULE OF ASSESSMENTS

Appendix 1: Schedule of Assessments

1. Screening

Subjects who Received Placebo or a Single Injection of ARCT-021 in Parent Study

Study Week/Day	D -28 to D -1
Visit Window (Days)	0
Informed Consent	X
Inclusion/Exclusion	X
Body Weight	X
Physical Exam ¹	X
Vital Signs ²	X
Pregnancy Test ³	X
Chemistry Panel	X
Hematology	X
Coagulation	X
HbA1c	X
Urinalysis ⁴	X
Immunogenicity ⁵	X
Drug/Alcohol Screen ⁶	X
SAE, CESI, NOCD and MAAE ⁷	X
Concomitant Medications and Procedures ⁸	X
SARS-CoV-2 questioning ⁹	X

1 Full physical exam

2 BP, HR, RR, temp

3 Women who are not surgically sterile or post-menopausal. Dipstick acceptable

4 Dipstick test per local procedures. If abnormal send sample to laboratory for microscopy.

5 This is only PRNT50 for the screening visit

6 Urine test.

7 SAE, CESI, NOCD and MAAE that occurred since completion of the Parent Study and screening for this study will be recorded. For subjects that received ARCT-021 in the Parent Study, these will be entered as SAE/CESI/MAAE in the EDC. For subjects that received placebo in the Parent Study these will be recorded as medical history.

8 Concomitant medications and procedures since completion of the Parent Study and screening for this study will be recorded for all subjects.

9 Subjects will be questioned about symptoms of COVID-19 and exposure to confirmed COVID-19 or confirmed SARS-CoV-2 infection cases amongst household contacts, friends, work contacts and other contacts.

Subjects who Received Two Injections of ARCT-021 in Parent Study

Study Week/Day	D -28 to D -1
Visit Window (Days)	0
Informed Consent	X
Inclusion/Exclusion	X
Body Weight	X
Physical Exam ¹	X
Vital Signs ²	X
SAE, CESI, NOCD and MAAE ³	X
Concomitant Medications and Procedures ⁴	X
SARS-CoV-2 questioning ⁵	X

- 1 Full physical exam (assessment of heart, lungs, abdomen, eyes, ears, nose and throat, head and neck, musculoskeletal, lymphatic, injection site, dermatologic, neurologic, extremities)
- 2 BP, HR, RR, temp
- 3 SAE, CESI, NOCD and MAAE that occurred since completion of the Parent Study and screening for this study will be recorded
- 4 Concomitant medications and procedures since completion of the Parent Study and screening for this study will be recorded
- 5 Subjects will be questioned about symptoms of COVID-19 and exposure to confirmed COVID-19 or confirmed SARS-CoV-2 infection cases amongst household contacts, friends, work contacts and other contacts.

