***Subjects that terminate early should complete all procedures for Study Day 281**

- 1 Abbreviated physical exam (assessment of vitals, heart, lungs, lymphatic, abdomen and symptom directed examination, if any symptoms) to be given during observation period to assess changes from screening.
- 2 BP, HR, RR, temp
- 3 Stored at -70 °C for follow up immunological assessments or exploration of laboratory findings and/or adverse events
- 4 SAE, CESI, NOCD and MAAEs will be recorded.
- 5 At each visit, subjects will be questioned about symptoms of COVID-19 and exposure to confirmed COVID-19 or confirmed SARS-CoV-2 infection cases amongst household contacts, friends, work contacts and other contacts.
- 6 Subjects that terminate from the study before completion will be told to inform the study site staff if they develop symptoms compatible with COVID-19 (Section 6.2.4) or a diagnosis of SARS-CoV-2 infection or COVID-19 for one year after vaccination so that they can be adequately followed up.

Subjects Receiving a Single Injection of ARCT-021 in This Study

Study Week/Day	Study Drug Administration	Post-Treatment Period (52 Weeks)							
		W1 D1	W2 D8	W3 D15	W5 D29	W9 D57	W25 D169	W37 D253	W53 D365/ Early Term*
Visit Window (Days)	0	±1	±1	0	±7	±14	±14	+14	
Physical Exam ¹	X ^a	X	X	X	X	X	X	X	X
Vital Signs ²	X ^a	X	X	X	X	X	X	X	X
Pregnancy Test ³	X ^a								
Chemistry Panel	X ^a	X	X	X					
Hematology	X ^a	X	X	X					
Coagulation	X								
HbA1c	X								
Urinalysis ⁴	X ^a	X		X					
Archived plasma sample ⁵	X ^a			X	X	X	X	X	X
Archived serum sample ⁵	X ^a			X	X	X	X	X	X
Archived PBMC sample ⁵	X ^a		X	X	X	X	X	X	X
Immunogenicity	X ^a			X	X	X			X
T-cell responses	X ^a		X	X		X			X
Drug/Alcohol Screen ⁶	X ^a								
Study Drug Administration	X								
Review of symptom diary ⁷		X	X						
Unsolicited AE	X	X	X	X					
SAE, CESI, NOCD and MAAE ⁸	X	X	X	X	X	X	X	X	X
Concomitant Medications and Procedures	X	X	X	X					
SARS-CoV-2 questioning ⁹	X	X	X	X	X	X	X	X	
Counselling about long-term follow-up for SARS-CoV-2 infection ¹⁰									X

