4. CHANGES TO PLANNED ANALYSIS

This is an unplanned interim analysis that was not anticipated at the time of study initiation and is being conducted to support a regulatory filing in [REDACTED] and other jurisdictions, as applicable. In addition, based on data availability in specific subgroups of participants in this study, further adjustments in the original protocol-specified analyses are made. These additional changes from the analyses described in the protocol are summarized below.

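### Cohort 2(A-D2) antibody summaries are conditional on PRNT50 seropositivity at screening, so they do not show persistence for all single-dose recipients, and no summary by parent cohort recombines the two halves

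*Protocol*

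**What the plan says.** The undosed group in the Protocol Synopsis is all two-dose recipients (E-H) plus those single-dose recipients, from parent cohorts A to D2, whose PRNT50 result at screening is positive. Protocol 3.2 and SAP 3.2 state the same rule. Seronegative single-dose recipients are dosed again and become Cohort 1b.

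Protocol 10.2 defines Cohort 2 as those "who were vaccinated with ARCT-021 in the parent study and who do not receive subsequent vaccination with ARCT-021 in the current extension study", with no mention of serostatus. SAP 5.2 splits 1b and Cohort 2 by parent cohort and describes 1b (D1) and 2 (D1) in the same words; likewise A, B, C and D2.

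In the screening schedule for placebo and single-injection participants (Protocol Appendix 1), the immunogenicity footnote reads "This is only PRNT50 for the screening visit". The two-injection screening schedule has no antibody test.

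Protocol 10.5.4 plans Cohort 2 antibody endpoints at extension Days 29, 197 and 281, which it equates to 6, 12 and 15 months from the last injection. SAP 5 and 7.3.1 give antibody results by cohort and sub-cohort. SAP 7.2 reports pseudovirus neutralization and MSD binding, not PRNT50. SAP 4 says this interim "is being conducted to support a regulatory filing".

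**The concern.** The secondary objective is long-term antibody response after vaccination. For single-dose recipients, antibody still detectable at screening decides who enters the rows that describe later antibody. With extension Day 1 at nominal parent Day 147 (SAP 5.3.2) and screening 1 to 28 days before it, that test falls at about Day 119 to 146.

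The rows 2(A) to 2(D2) carry dose-level names, so they invite reading as persistence by dose after one injection. They describe those still PRNT50-seropositive four to five months later. Parent-study results shown beside them are conditioned on the same later test, and those beside 1b are conditioned the other way. At this interim that arises mainly for D1 and D2; SAP Table 2 marks no parent-study data for A or C.

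E-H did not pass through this test. SAP Table 1 aligns A-D2 and E-H in the same 6- and 12-month columns, and a Cohort 2 total would average both. Dose differs as well: 1, 5, 7.5 and 10 mcg single-dose against 3 and 5 mcg two-dose.

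**Working it through.** **No plan figure to reproduce.** The documents give no sample size calculation, share seropositive, titer SD, LLOQ or cross-assay correlation. The calculation below shows direction and a plausible range only.

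**Is there a row that undoes the split?** SAP 7.3.1 ties antibody output to the SAP 5.2 cohorts and sub-cohorts. SAP 5 adds summaries by population, but not by parent cohort within it. Protocol 10.5.1 mentions dose level generically, and the Synopsis says results may be analysed by cumulative dose. None defines a summary of 1b(x) plus 2(x).

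**Effect of selection.** Assumptions: log screening PRNT50 and the log10 reported titer are bivariate normal with correlation r; the reported assay has log10 SD s; a share p is seropositive. Then

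GMT(selected) / GMT(all) = 10^(r × s × φ(z)/p), where z is the normal quantile of 1 − p.

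| p | φ(z)/p | r = 0.2, s = 0.4 | r = 0.8, s = 0.5 |
|---|---|---|---|
| 0.3 | 1.159 | 10^0.093 = 1.24 | 10^0.464 = 2.91 |
| 0.5 | 0.798 | 10^0.064 = 1.16 | 10^0.319 = 2.09 |
| 0.7 | 0.497 | 10^0.040 = 1.10 | 10^0.199 = 1.58 |
| 0.9 | 0.195 | 10^0.016 = 1.04 | 10^0.078 = 1.20 |

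At r = 0, or if everyone is seropositive, the ratio is 1.00. SAP 5.4 sets titers below LLOQ to LLOQ/2. Simulating that with 25% or 50% of all recipients below LLOQ lowers the ratios somewhat. The full ranges become about 1.2-2.9 (p = 0.3), 1.13-2.09 (0.5), 1.07-1.58 (0.7) and 1.03-1.20 (0.9). At p = 0.5 the percent above LLOQ is about 56-80% in the selected row where it is 50% in all, or 80-96% where it is 75%.

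**Can the halves be recombined?** SAP Table 2 marks extension Day 1 (pre-dose) for every 1b sub-cohort and extension Day 29 for every Cohort 2 sub-cohort. Pooling these by parent cohort leaves two opposing residuals.

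- *Offset.* Day 29 is nominal Day 175 in SAP Table 3 (SAP 7.2 says 176), so 1b is measured 175 − 147 = 28 days earlier. With an assumed half-life of 180 to 60 days, the decline is 2^(28/180) = 1.11 to 2^(28/60) = 1.38. If half are in 1b, the pooled GMT is high by the square root of these, 1.06 to 1.18.
- *Censoring.* Results after an off-study vaccine or evidence of infection are censored (SAP 5.3.3, 7.3). This falls more on Cohort 2, which is measured later. The exclusion for other SARS-CoV-2 vaccines also sits under "Only for subjects that will receive ARCT-021 in this study", so Cohort 2 members may already have had one. With p = 0.5 and an assumed 30% of Cohort 2 censored at random, Cohort 2 is 0.35/0.85 = 0.412 of the pool. The mean log10 titer shifts by (0.412 − 0.588) × r × s × 0.798, a ratio of 0.88 to 0.97. At 50% censored the Cohort 2 share is 0.25/0.75 = 0.333 and the ratio is 0.78 to 0.95.

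Combined at 30% censored, the 1b share is 0.588 and the offset factor is 1.11^0.588 = 1.07 to 1.38^0.588 = 1.21. The net ratio then runs from 0.88 × 1.07 = 0.94 to 0.97 × 1.21 = 1.17. Its direction is unknown.

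**The case against.** The rows describe correctly the group they name, the split is stated in SAP 3.2, and the analysis is descriptive. Sub-cohort rows already show A-D2 apart from E-H, and without table shells a blended Cohort 2 total is not certain. Cohort 1a gives a 7.5 µg single-dose series not selected on vaccine response. Further cohorts may be added in a final SAP that was not supplied. All this stands and limits the point to interpretation. It does not remove the conditioning within 2(A) to 2(D2), and identical sub-cohort descriptions conceal it.

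Four stronger readings are tempting but unsupported:

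- A reader might infer that the rows are inflated by a known amount. Selection is on PRNT50 while other assays are reported, and no correlation is given.
- A reader might call the pooled 1b-plus-2 row unselected, and only slightly high. Seronegatives who fail the criteria that apply only to those being dosed (Protocol 5.1, 5.2) are screen failures (3.8.1) and appear in neither half, and censoring pulls the other way from the offset.
- A reader might take E-H as fully unselected. They escape this serostatus split, but still had to complete the parent study and roll over, and they are also censored.
- A reader might suppose that SAP Table 2 already holds everything needed. Neither it nor SAP Appendix B includes the screening PRNT50 result.

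The disagreement between the SAP 4.4 text and Table 2 over which Cohort 2 sub-cohorts have parent-study data is a separate matter and is no evidence for this one.

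**Conclusion.** The point holds. The selection follows from the dosing rule. The direction, overstatement relative to all single-dose recipients, follows only if screening PRNT50 correlates positively with the reported assays and some participants were seronegative. The size is not computable; the ratios above rest wholly on assumed inputs and estimate no planned table. No formal comparison is affected. What is at risk is a reader of a filing-support interim taking 2(A) to 2(D2) as single-dose persistence, or setting them against 2(E-H). This should be changed, but it does not invalidate the analysis.

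**What to change.** 1. Label all 2(A-D2) antibody results, including 12 and 15 months, *conditional on PRNT50 seropositivity at screening*. Give A-D2 and E-H separately in place of a single Cohort 2 antibody total.
2. By parent cohort, report the number and percent PRNT50-seropositive at screening among all screened single-dose participants. The result is collected (Protocol Appendix 1) but must be added to the interim data.
3. For D1 and D2, add parent-study time points pooled over 1b and 2, once the SAP 4.4 text and Table 2 are reconciled.
4. As a supportive table by parent cohort, pool 1b pre-dose Day 1 with Cohort 2 Day 29 on the same assay. Give GMT or GMC, percent above LLOQ, and the number contributing and censored in each part. Title it *pooled over screening serostatus among enrolled participants* and state that the net residual direction is unknown. If GMFR is shown for D1/D2, say that it uses parent Day 1, a supplementary baseline for 1b that differs from Protocol 10.3 and SAP 5.3.1. Archived Cohort 2 Day 1 serum, kept "for follow up immunological assessments or exploration of laboratory findings and/or adverse events", could remove the 28-day offset at extra assay cost.
5. Point to Cohort 1a for 7.5 µg single-dose persistence not selected on vaccine response, noting that its later data are also subject to off-study-vaccine censoring.

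SAP 5.1 bars changes after the data pull; if that has passed, add the tables as labelled post hoc output. The cost is a few tables, one added variable, small numbers per parent cohort and possibly less favourable persistence figures.
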